**PI- List drop down**

[DP:1]

**Px0.** Please select your primary setting of practice

- Blood bank
- Transfusion centre
- Blood donation centre
- Private office/ Clinic
- Academic/ University hospital
- District General/ Community / Non-Teaching Public Hospital
- Private hospital
- Other, specify \_\_\_\_\_

**PI – List Drop Down**

[DP:1]

**Px1.** Please select if your primary setting at the office, clinic or hospital is one of the below

- Blood bank
- Transfusion centre
- Blood donation centre
- None of the above

PI- show if Px0= Private office/ Clinic, Academic/ University hospital, District General/ Community / Non-Teaching Public Hospital, Private hospital

**Px2.** Have you provided blood products to a Multiple Myeloma patient treated with **isatuximab**?

- Provided blood products on a regular basis
- Provided blood products at least once

- Have never provided blood products

PI- List drop down

[DP:1]

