### Inclusion Criteria

- The HCP is involved in the management and follow-up of multiple myeloma, such as oncology/haematology specialists and HCPs associated with blood banks/transfusion centres who have not necessarily prescribed isatuximab.
  - Prescribers (Oncologists/Haematologists): The HCP has prescribed isatuximab at least once.
  - Non-prescribers (Blood banks/transfusion centres): The HCP has provided blood products at least once for a patient treated with isatuximab.
- The HCP provides consent to participate.

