## 9.2.3 HCP Recruitment

Recruitment of HCPs will occur mainly from a multi-national panel (the LiveTracker™ panel). LiveTracker™ is a cloud-based, real-time, continuous electronic data collection platform that allows collection of real-world evidence data from HCPs across multiple continents. Multi-national panels of physicians in LiveTracker™ exist across haematology-oncology therapeutic areas, including a panel for MM. In order to optimise recruitment, educational material distribution lists will be used when possible as a complement.

To be part of the LiveTracker™ physician panel, physicians are screened, including a credentials check, and fill out an initial profiling survey that includes answering questions about practice setting, caseload, specialities, etc. For participation in this study, HCPs will be screened based on the following criteria to identify qualified participants:

- 1) Prescribers: haematologist/onco-haematologist who prescribed isatuximab at least once.

The prescribers are medical specialists who are responsible for initiating the treatment, communicate with the patient and make the appropriate decision(s) if a transfusion is needed. Depending on the country, they initiate the blood compatibility profile,

manage the transfusion, including the order of blood products or refer the patient to a transfusion department / blood bank.

- 2) Non-prescribers: HCPs work in the blood banks/transfusion centres who have provided blood products at least once for a patient treated with isatuximab.

Depending on the country, HCPs affiliated with transfusion departments or blood bank may oversee the blood compatibility profile, identify and deliver the blood products. However, in most countries, they do not communicate with the patient.

The potential pool of HCP participants is shown in Table 2, which is mainly based on the current number of HCPs in the haematologist and haemato-oncologist panels in LiveTracker™. LiveTracker™ is actively building up a panel of HCPs working in the blood banks/transfusion centres to have sufficient number of HCPs to send invitation emails to, as presented in Table 3 Column C.

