**Screening criteria: Screen-in if**

- “Prescribe on a regular basis” or “at least once” on question Px
- OR**
- “Provided blood products on a regular basis” or “at least once” on question Px2.

-----Page Break-----

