**Questions for Prescribers**

PI- Show if Px= “Prescribe on a regular basis” or “at least once”

- 1 **Have you received the educational material from Sanofi regarding the minimization of risk associated with isatuximab?**
  - Yes
  - No

PI- List drop down

[DP:1]

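### Appendix C screens and routes respondents without using practice setting, so it does not implement the protocol's own definition of a non-prescriber

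*Protocol*

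**What the plan says.** **Definition.** Section 9.2.2 gives the non-prescriber criterion as "Non-prescribers (Blood banks/transfusion centres): The HCP has provided blood products at least once for a patient treated with isatuximab". Section 9.2.3 repeats both conditions, setting and supply: "Non-prescribers: HCPs work in the blood banks/transfusion centres who have provided blood products at least once for a patient treated with isatuximab". Prescribers are defined in Section 9.2.2 only by having prescribed isatuximab at least once; no setting is excluded.

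**Questionnaire (Appendix C).**
- Px asks about adoption of isatuximab.
- Px0 asks for the primary practice setting.
- Px1 is shown only to those who chose an office, clinic or one of the hospital types at Px0: "Please select if your primary setting at the office, clinic or hospital is one of the below".
- Px2 asks: "Have you provided blood products to a Multiple Myeloma patient treated with" isatuximab. Unlike Px1, it has no display condition.
- Under "Screening criteria: Screen-in if", the rule is a positive Px or a positive Px2.
- The prescriber module carries the instruction "PI- Show if Px= “Prescribe on a regular basis” or “at least once".
- The non-prescriber module is conditioned only on "Provided blood products on a regular basis” or “at least once” on question Px2".

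**Use of the groups.** Section 9.7.4 analyses the two HCP types separately and sets an 80% threshold for each on its own behaviour questions (five of seven for prescribers, two of three for non-prescribers). These are joined by AND to an 80% threshold on the key knowledge question. Table 3 targets 300–360 prescribers and 40–100 non-prescribers.

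**The concern.** The protocol defines a non-prescriber by two conditions, and the instrument applies one. Setting is collected but appears in neither the screen-in rule nor the routing.

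Two things follow from the written logic alone. First, an HCP who never prescribed isatuximab and works outside a blood bank or transfusion centre fails Section 9.2.2, yet enters as a non-prescriber on a yes to Px2. Second, an HCP positive on both Px and Px2 meets both modules' display conditions, and no rule says which applies or in which group the person counts.

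The non-prescriber behaviour questions, on urgent units, DTT and Kell, are written for blood-bank staff. That group is the smaller of the two, and because the criteria are joined by AND, missing its threshold alone means the overall standard is not met. Under dual routing an HCP would also see the key knowledge question twice. Since Section 9.6.1 counts a survey as valid only when every question is completed, a prescriber who stopped in the second module might not count as a valid respondent at all.

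**Working it through.** **1. The plan's own figures.** Table 3 totals: 10–25% × 400 = 40–100 non-prescribers and 75–90% × 400 = 300–360 prescribers. Both reproduce. The sample size also reproduces: 1.96² × 0.5 × 0.5 / 0.05² = 384.16, stated as 384 (95% confidence assumed, as Section 9.5 does not state the level). This point does not affect it.

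**2. Routing as written.** Cross the four Px answers, the three Px2 answers and four setting classes: blood bank, transfusion or donation centre at Px0; hospital or office with such a unit at Px1; hospital or office with none; Other. That gives 4 × 3 × 4 = 48 combinations.

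| Px | Px2 | Screened in | Module shown, whatever the setting | Combinations |
|---|---|---|---|---|
| has prescribed | yes | yes | both | 16 |
| has prescribed | never | yes | prescriber | 8 |
| never prescribed | yes | yes | non-prescriber | 16 |
| never prescribed | never | no | none | 8 |

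Each setting class contributes the same counts (4, 2, 4, 2), so setting has no effect on the outcome. These are logical cases, not expected numbers of respondents.

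**3. Size of dual routing, under an assumption.** The documents give no rate of yes to Px2 among prescribers. Assume d = 5–10%, with P prescribers and N true non-prescribers. The number added is k = d × P, and its share of the enlarged non-prescriber set is k / (N + k).

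| P | N | d | k | Share |
|---|---|---|---|---|
| 360 | 40 | 5% | 18 | 18/58 = 31% |
| 360 | 40 | 10% | 36 | 36/76 = 47% |
| 300 | 100 | 5% | 15 | 15/115 = 13% |
| 300 | 100 | 10% | 30 | 30/130 = 23% |

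**4. What that could do to the 80% criterion.** The observed rate is (N × a + k × b) / (N + k), where a and b are the pass rates of true non-prescribers and misrouted respondents. For illustration only, take a = 85% and b = 60%; neither figure is in the documents.
- N = 40, k = 18: (34 + 10.8)/58 = 77%
- N = 40, k = 36: (34 + 21.6)/76 = 73%
- N = 100, k = 15: (85 + 9)/115 = 82%
- N = 100, k = 30: (85 + 18)/130 = 79%

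Under these rates the result drops below 80% once k exceeds N/4, because 0.85N + 0.60k < 0.80(N + k) gives 0.05N < 0.20k. That is more than 10 misrouted respondents when N = 40, or more than 25 when N = 100. If b were above a, the shift would go the other way. Steps 3 and 4 suppose that every dual-positive HCP is counted as a non-prescriber.

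**The case against.** The strongest reply has four parts.

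**Wording of Px2.** Section 7 speaks of providing blood product only for blood-bank and transfusion staff. Section 9.2.3 says that, depending on the country, prescribers "manage the transfusion, including the order of blood products or refer the patient to a transfusion department / blood bank", while blood-bank staff identify and deliver the products. Ordering is not providing, so few clinicians may say yes. This limits the likely frequency. But Px2 does not define the term, and a clinician who arranged a transfusion could reasonably answer yes.

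**Other screens.** Section 9.2.3 says HCPs will be screened on criteria that include setting, panel members are profiled, and Table 3 plans invitations by HCP type. These may reduce misrouting, but nothing in the text links them to the Appendix C rules.

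**Repair at analysis.** Px, Px0 and Px1 are recorded under a unique identifier, so an SAP rule could reassign or exclude respondents. This stands in part, and for that reason a reader who infers that dual-positive HCPs will be counted in both denominators goes beyond the documents. A later rule could not change who was screened in, who counted towards recruitment or who saw which module. Section 9.9 also rules out recontact to clarify or revise answers.

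**Frequency.** A reader might infer that many prescribers will fall into both groups; no figure supports this. One might also try to size the never-prescriber route from Section 9.2.3: 17% of 4,500–8,100 prescriber invitations is 765–1,377 replies, of which 60–74%, or 459–1,019, do not become eligible completers. That pool cannot be read as never-prescribers, because the 26–40% is the share who are both eligible and complete, so its complement includes eligible HCPs who drop out. The share of the pool saying yes to Px2 is also unknown.

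**Conclusion.** The point holds as a contradiction between Sections 9.2.2 and 9.2.3 and the screening and routing rules in Appendix C. Followed as written, the questionnaire can admit respondents whom the protocol excludes, and it leaves HCPs positive on both Px and Px2 without a defined group. This needs no assumption.

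The size is not known. The 15–36 added respondents rest on an assumed 5–10% of 300–360 prescribers answering yes to Px2 and being counted as non-prescribers. The effect on the pass rate rests further on assumed pass rates. What the documents do establish is that the group is small (40–100) and carries its own 80% criterion, so it has little room to absorb misrouting. The rules should be reconciled before the survey goes live.

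**What to change.** In Appendix C:
- Make non-prescriber screen-in and routing require both an eligible setting at Px0 or Px1 (blood bank or transfusion centre) and a positive Px2. State whether blood donation centres count: Px0 and Px1 list them and Table 1 notes their role in Switzerland, but Section 9.2.2 does not name them.
- Show Px1 also when Px0 is Other. At present those respondents never see it, and transfusion staff who chose Other could be lost under the new rule.
- Keep prescriber eligibility as a positive Px with no setting condition. Excluding blood-bank settings there would contradict Section 9.2.2 and could remove an eligible prescriber based in a transfusion centre.
- Add a pre-specified priority rule so that an HCP who qualifies for both groups is routed to, and counted in, exactly one.

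Under these rules no one sees both modules, and never-prescribers outside an eligible setting are screened out. The sample size of 384 does not change. The cost is survey programming on questions already asked, plus somewhat fewer HCPs screening in as non-prescribers; the documents do not allow that number to be estimated.

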**Screening criteria: Screen-in if**

- “Prescribe on a regular basis” or “at least once” on question Px
- OR**
- “Provided blood products on a regular basis” or “at least once” on question Px2.

-----Page Break-----

**Questions for Prescribers**

PI- Show if Px= “Prescribe on a regular basis” or “at least once”

- 1 **Have you received the educational material from Sanofi regarding the minimization of risk associated with isatuximab?**
  - Yes
  - No

PI- List drop down

[DP:1]

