## 9.2 Setting

The study will be conducted in selected European countries after the launch of isatuximab (SARCLISA) and the distribution of the educational materials to the HCPs (see Table 1). Up to 9 countries may be included in this study, where country inclusion will be based on:

- Isatuximab launch dates
- Date of distribution of the educational materials
- Target population size (oncology centres and blood banks)
- Feasibility in terms of regulatory implementation at national level
- Representativeness of Europe
  - Country population size
  - Country geographic location

Table 1 - List of launch date and distribution status of educational materials in each country

Country	Actual/Estimated Launch Date	Implementation of EMs	Recipients	Comments
Switzerland	30 APR 2020	JUN 2020 (digital) AUG 2020 (hardcopies) JUN 2021 (website)	About 50 maximum physicians in Onco/Haematology, blood banks (BB) and blood donation centres	Hospitals have either their own BB or work with a centralized one. In some cases, there is no BB and this is covered by the Blood donation center
Austria	JUL 2020	JUN- 2020 (hardcopies) Distribution of the revised version completed in July 2021	29 Internal Medicine, 16 Oncology, 9 Haemato-Oncology, 1 Haematology, 2 immunology serology transfusion medicine, 9 Blood bank transfusion medicine, regional blood donation centre, and 58 hospital pharmacies (for information)	Oncologists and Haematologists are specialised sub-units of Internal Medicine

Country	Actual/Estimated Launch Date	Implementation of EMs	Recipients	Comments
France	SEP 2020 (post ATU*)	AUG 2020 Distribution of the revised version planned to be completed by 31Dec2021	778 Oncologists + 2,002 Haematologists + national centre of BB from where EMs will be forwarded to the 13 regional centres.	Based on ATU* experience (Aug 2019, 399 patients), Haematologists made most of prescriptions.
Sweden	01-JUL- 2020 (not reimbursed)	JUN 2020 (mail+ website)  Distribution of the revised version completed in June 2021	Haematologists (293) Head of Haematologist Department, BB and transfusion centres (104)	All prescriptions by Haematologists
Finland	15 SEP 2020 (not reimbursed)	SEP / OCT and NOV 2020 + ad hoc distribution in Q1/Q2 2021 (email and mail)  Distribution of the revised version completed in Sep 2021	Haematologist (76), BB (10)	All prescriptions by Haematologists

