The Netherlands	OCT 2020 (reimbursed)	SEP 2020 (mail + website)	1,335 Oncologists / Haematologists + 631 hospital pharmacists + 350 clinical chemists (all HCPs in-training included) and 21 blood banks relevant societies for professionals	
UK	01 JUN 2020	APR-AUG 2020 (mail)	N=5061	
Poland		AUG-SEP 2020 (email, mail and website) Distribution of the revised version completed in Sep 2021	Physicians: haematologists (326), oncologists (705), specialists in transfusiology (97). National and regional consultants in haematology, oncology and transfusiology (48).	

Country	Actual/Estimated Launch Date	Implementation of EMs	Recipients	Comments
			Multiple myeloma treatment centres (53). Regional and field blood-donation centres (163).	
Germany	01 MAR 2021	JAN -MAR 2021 (mail and website)  Distribution of the revised version completed in June 2021	Oncologists and haematologists: 3655  Blood banks: 170	
Italy	29 MAR 2021	APR 2021 (email)	Haematologist, oncologists and scientific societies: 10 107	
Hungary	Planned NOV 2021	No distribution (product not yet launched)	To be provided later	

\* ATU: temporary authorisation for use ‘autorisation temporaire d’utilisation”

Abbreviations: BB = Blood Banks; EM = Educational Materials; HCP = healthcare professional; UK = United Kingdom

Since country inclusion is based on the date of launch and distribution of the educational materials, target population size, and representativeness of Europe, we will include, at minimum, the following five countries: France, Switzerland, Austria, Sweden, and the Netherlands. There will be a maximum of nine countries included in this study and the other potential countries include (but are not restricted to): Germany, Finland, United Kingdom (UK), Italy, Poland and Hungary. Also, the necessary Ethics/Regulatory requirements to conduct this study may generate some changes in this list.

Current countries listed are the ones with educational materials expected to be implemented by the end of 2021 (Table 1) as data collection will occur in each country 12-18 months post-implementation. The following EU countries cannot participate because SARCLISA (isatuximab) will not be marketed or educational materials will not be implemented by the end of 2021 in order to complete data collection by Q1 2023: Bulgaria, Cyprus, Estonia, Greece, Ireland, Latvia, Lithuania, Spain and Romania.

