### **9.3.2 Implementation**

All HCPs:

- Reception of the education materials (brochure and maybe Patient Card depending on the type of HCPs).

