### **9.7.6 Subgroup Analyses**

In addition to the analyses by HCP type (prescribers and non-prescribers) as described above, analyses will also be performed at country level.

Other sub-groups analysis will include (if sample size allows):

- Characteristics of responders who provided correct answers to 70%, 80%, 90% and 100% of the questions vs responders who did not reach the threshold
- Comparison of responders and non-responder's characteristics
- Comparison of responders and overall target population characteristics
- Analyses among HCPs who actually received the EMs vs. those who did not.

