## Questions for Non-prescribers

“Provided blood products on a regular basis” or “at least once” on question Px2.

**1 Have you received the educational material from Sanofi regarding the minimization of a risk associated with isatuximab?**

- Yes
- No

PI- List drop down

[DP:1]

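### The receipt item asks only about material 'from Sanofi', which is narrower than the implementation variable and may miss HCPs reached by forwarding, through their institution or via a website

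*Protocol*

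**What the plan says.** **The variable.** Protocol section 9.3.2 lists, for all HCPs, "Reception of the education materials (brochure and maybe Patient Card depending on the type of HCPs". It sets no condition on who supplied the materials.

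**The item.** In Appendix C, Q1 for prescribers reads "Have you received the educational material from Sanofi regarding the minimization of risk associated with isatuximab" and Q1 for non-prescribers reads "Have you received the educational material from Sanofi regarding the minimization of a risk associated with isatuximab". Both offer Yes and No only. Neither asks about the channel, neither separates the brochure from the Patient Card, and neither allows an uncertain answer. No other item in either branch measures receipt.

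**The distribution.** Table 1 in section 9.2 gives the routes by country. For French blood banks the recipient is a "national centre of BB from where EMs will be forwarded to the 13 regional centres". For the Netherlands the list includes "21 blood banks relevant societies for professionals", and for Italy "Haematologist, oncologists and scientific societies: 10 107". Websites appear as a channel in five countries (Switzerland, Sweden, the Netherlands, Poland and Germany), for example "JUN 2020 (mail+ website" in Sweden.

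**The use.** Section 9.7.6 plans, if sample size allows, "Analyses among HCPs who actually received the EMs vs. those who did not".

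**The concern.** The item is narrower than the variable it is meant to measure. A blood-bank HCP whose copy came from the regional centre or the employer, or who read the material online, can reasonably say that nothing was received from Sanofi. That answer would be recorded as not reached.

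Two results depend on the item. One is the respondent-level receipt rate, which is what the survey contributes to objective 1. The other is the received versus not-received comparison, the only contrast within the study between HCPs with and without the materials. False No answers lower the first. They also put HCPs who had the materials into the comparison group of the second. Because the routes differ by country and HCP type, the error would be uneven.

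It could not be corrected afterwards. Recruitment is mainly from the LiveTracker panel, with distribution lists only as a complement (section 9.2.3), and the data are anonymous to the sponsor (section 10.2). The protocol describes no link between a respondent's answer and the distribution records. Section 9.9 asks for implementation results to be read against each country's distribution strategy, but no channel is recorded that would allow this for individual respondents.

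**Working it through.** No figure in the protocol is in dispute, so the main check is to compare the texts. The arithmetic after it only shows how the error would behave.

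**1. Item against variable.** Section 9.3.2: reception, any sender. Appendix C Q1, both branches: reception from Sanofi. The item is narrower on its natural reading.

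**2. Item against Table 1.**
- *Documented forwarding:* French blood banks (a national centre passing material to 13 regional centres). This concerns non-prescribers.
- *Delivery listed by institution:* blood banks in Finland (10), the Netherlands (21) and Germany (170), and regional and field blood-donation centres in Poland (163). Sweden lists blood banks and transfusion centres, with department heads, in an entry of 104. The survey respondents are individuals.
- *Website:* five countries, in each case alongside mail, email, digital or hard-copy delivery. Whose websites they are is not stated.
- *Societies:* named as recipients in the Netherlands and Italy. Onward distribution is not stated.
- *Prescribers:* mostly listed as direct recipients (for example 778 oncologists and 2,002 haematologists in France), so for them the website is the main indirect route.

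**3. Effect on the receipt rate.** Let R be true receipt, s the share of reached HCPs served only by an indirect route, and f the share of those who answer No because of the wording. All three are assumptions; the protocol gives none of them.

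Observed receipt = R × (1 − s × f). With R = 80%:
- f = 0: 80%, no error
- s = 10%, f = 25%: 0.80 × (1 − 0.025) = 78%
- s = 25%, f = 50%: 0.80 × (1 − 0.125) = 70%
- s = 50%, f = 100%: 0.80 × (1 − 0.50) = 40%

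**4. Effect on the 9.7.6 contrast.** The share of the No group that in fact had the materials is c = R s f / (1 − R + R s f). If misclassified HCPs answer like other HCPs who had the materials, the observed difference is the true difference × (1 − c). Assume 90% correct with the materials and 60% without, a true difference of 30 points:
- s = 10%, f = 25%: c = 0.02/0.22 = 9%; 30 × (1 − 0.02/0.22) = 27 points
- s = 25%, f = 50%: c = 0.10/0.30 = one third; the No group scores (2/3) × 60 + (1/3) × 90 = 70, so 20 points are observed
- s = 50%, f = 100%: c = 0.40/0.60 = two thirds; 10 points

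**5. Ceiling from French forwarding alone.** Table 3 plans 5–18 French non-prescribers. Against the stated total of 40–100 this is 5/40 = 12.5% to 18/100 = 18%. Against the sum of the eleven country rows (27–97) it is 5/27 = 18.5% to 18/97 = 18.6%. The non-prescriber receipt rate could fall by that many points only if every French non-prescriber was reached, all of them solely by forwarding, and all answered No. At most nine countries will take part, so the row sums are themselves only indicative.

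**The case against.** The strongest reply is that the phrase can be read as describing Sanofi's material whatever the route. The brochure directs readers to Sanofi and the Patient Card carries its name, so a forwarded copy is recognisable. This stands: a reader might infer that indirectly reached HCPs will be counted as not reached, but the documents support only that they may be. The ambiguity is still a defect, since respondents can resolve it differently.

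It also stands that Table 1 does not show distribution to be largely indirect. Forwarding is documented only for French blood banks. Societies are listed as recipients, not as distributors, and the websites may be Sanofi's own.

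A reader might further infer that Q1 is the study's whole measure of implementation. It is not. Section 9.7.4 also describes delivery against plan at country level, although that description does not show whether individual respondents were reached.

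Finally, the consequences are bounded. None of the three 80% criteria in 9.7.4 uses Q1, the 9.7.6 comparison is conditional on sample size, and the study is descriptive. The caveat in 9.9 covers variation in distribution strategy but not the wording of the item. The pilot interviews in 9.4 could bring the problem to light, but the protocol does not direct them to it.

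**Conclusion.** The mismatch between Q1 and section 9.3.2 is real and affects both branches, most clearly the non-prescriber one. It may understate receipt, unevenly by country and HCP type, and may shrink the received versus not-received difference.

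The size is unknown and could be nil, because it depends on how many HCPs were reached only indirectly and on how they read the question. The 12–19 points from France in the working is a worst case and not an estimate, and the dilution figures rest entirely on assumed inputs. The success criteria are unaffected. The point is worth acting on because the error cannot be repaired after data collection and the remedy is small.

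**What to change.** Before the pilot, reword Q1 in both branches to ask whether the HCP has received or consulted the isatuximab educational material (brochure; Patient Card where applicable) by any route. Offer these options, with more than one channel allowed:
- directly from Sanofi
- forwarded by my institution, blood service or department
- from a society
- from a website
- not received
- do not recall

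Count any route as received, report receipt by channel and country, and define the 9.7.6 subgroup on this variable. Keep do-not-recall as its own category. In the pilot interviews, ask participants how they understood the item.

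Do not show the brochure cover or title as a memory aid. The cover (Appendix A) states that the product interferes with blood typing, and the next item, Q2, is the key true/false question on that risk. Showing it would give away the answer to the first success criterion.

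The cost is one longer item and its translations.
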